## 8. Blinding Integrity and Control Measures

- Post-treatment, participants will guess their treatment group to assess blinding effectiveness. Medication changes will be monitored to ensure consistency.

## 9. Handling Missing Data and Sensitivity Analysis

- **Imputation:** Apply multiple imputation if the missing rate is above 10%.
- **Sensitivity Analysis:** Compare results with and without LOCF to ensure robust findings.

This statistical plan aligns with the study objectives and incorporates the additional neurophysiological and data management details.

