### 3. Sample Size and Power

- **Primary Outcome:** Pain severity on the Visual Analogue Scale (VAS).
- **Secondary Outcomes:** Questionnaire measures (MFIS, PSQI, BDI, PCS, MGPQ, PVAQ) and neurophysiological measures (LEP, EEG, rsfMRI).
- **Sample Size:** 60 participants (30 per group), allowing an 80% power to detect a 1.1 cm difference on the VAS scale (Cohen's d effect size) with a significance level of 0.05. The design anticipates a 10% dropout rate.

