### 6. Statistical Analysis Plan

#### A. Primary Outcome Analysis: Pain Severity (VAS)

- **Modeling:** Mixed-effects repeated-measures ANOVA with group (treatment vs. sham) as a between-subjects factor and time (baseline, immediate post-treatment, 4-week, 12-week, 24-week) as a within-subjects factor.
- **Post-Hoc Tests:** Bonferroni-adjusted post-hoc tests will examine specific time points if interaction effects are significant.
- **Intention-to-Treat (ITT) and Per-Protocol Analyses:**
  - **ITT:** Last observation carried forward (LOCF) for missing data.
  - **Per-Protocol:** Include only participants with at least 8 out of 10 therapy sessions completed and no interfering medications.

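### The one named sensitivity analysis, VAS results with and without LOCF, cannot test for unrecorded loss of benefit among active-arm leavers, so agreement between the two would not show robustness

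*SAP*

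**What the plan says.** The intention-to-treat rule for the primary outcome (SAP section 6A) is: "Last observation carried forward (LOCF) for missing data". The model is a "Mixed-effects repeated-measures ANOVA with group (treatment vs. sham) as a between-subjects factor" and time over five assessments, the last at 24 weeks.

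Section 9 adds two provisions. One is conditional imputation: "Apply multiple imputation if the missing rate is above 10" per cent. The imputation model, its assumption, how the missing rate is counted and the role of the result are not stated. The other is the only item labelled a sensitivity analysis: "Compare results with and without LOCF to ensure robust findings". Without LOCF could mean completers, all observed data or multiple imputation; the SAP does not say which.

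Section 6A also has a per-protocol analysis: "Include only participants with at least 8 out of 10 therapy sessions completed and no interfering medications". On expected loss, section 3 says: "The design anticipates a 10% dropout rate".

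The closing section on deviations from the plan reports that the trial was discontinued because of COVID-19, that only descriptive statistics can be given for now, and that resumption is being explored.

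**The concern.** The protocol's first aim is long-term pain suppression. Stimulation lasts two weeks and follow-up runs to 24 weeks, with gaps of 8 weeks (week 4 to 12) and 12 weeks (week 12 to 24) between the later visits. Pain can return within such a gap, and a participant can stop attending before anyone measures it. The protocol's section on minimizing risks lists loss to follow-up and withdrawal by the participant among the reasons for termination.

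For such a participant, LOCF keeps the last, better score. An observed-case analysis drops the person at week 24. Imputation under MAR predicts the score from participants in the same arm who had similar earlier scores and stayed. None of these lets the leaver do worse than the observed data suggest, so all three can be wrong together. A reader told that results agreed with and without LOCF would take this as support for the week-24 effect, although the assumption that matters was never varied. The choice of primary method does not alter this: with a mixed model or multiple imputation as primary, the same comparison would still leave it untested.

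**Working it through.** **1. The plan's own figure.** Section 3 gives "60 participants (30 per group), allowing an 80% power to detect a 1.1 cm difference on the VAS scale" "with a significance level of 0.05". No SD is stated, so the sample size cannot be checked independently. Solving for the SD, assuming a two-sided test and 27 evaluable per arm (30 less 10%):

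- d = (1.960 + 0.842) × √(2/27) = 0.7625, so SD = 1.1 / 0.7625 = 1.44 cm.
- With all 30 per arm evaluable, d = 0.7234 and SD = 1.52 cm.

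SD 1.44 cm returns 27 per arm, and 54 / 0.9 = 60, so the figure is attainable. This SD is used below as an assumption.

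**2. Loss of benefit not recorded before dropout.** Assumptions, none of them in the documents: sham is unchanged; active stayers keep 1.1 cm; a share p of the active arm shows 1.1 cm at the last attended visit and has none at week 24.

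- True effect = (1 − p) × 1.1
- LOCF = (1 − p) × 1.1 + p × 1.1 = 1.1
- Observed cases = 1.1
- Shared bias = p × 1.1

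| p, active arm | True (cm) | LOCF | Observed cases | MAR | Shared bias |
|---|---|---|---|---|---|
| 10% | 0.99 | 1.10 | 1.10 | 1.10 | 0.11 |
| 20% | 0.88 | 1.10 | 1.10 | 1.10 | 0.22 |
| 30% | 0.77 | 1.10 | 1.10 | 1.10 | 0.33 |

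The MAR column comes from simulation (200,000 per arm, SD 1.44 cm, within-person correlation 0.6, loss at a random follow-up visit, regression imputation by arm). The simulation also reproduced the other columns.

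The planned 10% dropout is six participants. Split equally, that is 3 of 30 active (10%, bias 0.11 cm). If all six were active it is 6 of 30 (20%, bias 0.22 cm). In both cases the overall rate is exactly 10%, so a trigger set above 10% would not start multiple imputation if the rate is counted over participants.

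**3. Loss recorded at one visit, then dropout.** Same simulation, except that one worse score is recorded before the participant stops. Those who lose benefit at week 24 itself are observed, so fewer scores are missing.

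| Active arm losing benefit | Active missing at week 24 | True (cm) | LOCF | Observed cases | MAR |
|---|---|---|---|---|---|
| 10% | 6.6% | 0.99 | 0.99 | 1.06 | 1.04 |
| 20% | 13.3% | 0.88 | 0.88 | 1.02 | 0.98 |
| 30% | 20.1% | 0.76 | 0.77 | 0.96 | 0.90 |

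Here LOCF is about right and the analyses separate on average.

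**4. What agreement would mean at this trial's size.** In 4,000 simulated trials per setting with 30 per arm, LOCF and observed-case estimates lay within 0.3 cm of each other as follows:

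| Active arm losing benefit | Unrecorded (both biased) | Recorded (LOCF about right) |
|---|---|---|
| 20% | 98% | 91% |
| 30% | 94% | 80% |

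Under these assumptions agreement is common in both cases, and more common when both estimates are wrong.

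**5. What a delta adjustment would show.** Raise imputed VAS scores by δ where a share p_A of the active arm and p_S of the sham arm is missing. From a MAR estimate of 1.10 cm the adjusted effect is 1.10 − p_A × δ + p_S × δ. For the active arm only:

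- 10% missing, δ = 1.1: 1.10 − 0.11 = 0.99 cm, the true value in step 2. With δ = 2.0: 0.90 cm.
- 20% missing, δ = 1.1: 0.88 cm. With δ = 2.0: 0.70 cm.

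A rough two-sided significance threshold is 1.96 × 1.44 × √(2/30) = 0.73 cm, ignoring imputation variance and repeated measures. A 1.10 cm result would then tip at δ = 0.37 / 0.20 = 1.85 cm with 20% missing, but only at 0.37 / 0.10 = 3.7 cm with 10% missing.

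**The case against.** The strongest reply is that the shared error follows from the inputs in step 2 and is not a general property of the comparison. That is right, and it limits the point in several ways.

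- A reader might infer that the two analyses always err together. The documents do not support this. VAS is taken after treatment and at 4, 12 and 24 weeks, and the protocol adds a 1-week visit, so a relapse may well be recorded before someone leaves. Step 3 then applies.
- A reader might infer that the check is worthless. It does respond to waning among stayers. If stayers fall to 0.55 cm and 20% of the active arm left at 1.1 cm, LOCF gives 0.8 × 0.55 + 0.2 × 1.1 = 0.66 cm and stayers alone give 0.55 cm.
- A reader might infer that the week-24 effect is bound to be overstated. The direction depends on the arm. If 20% of sham participants worsen by 1.1 cm unrecorded and leave, the truth is 1.1 + 0.22 = 1.32 cm and both analyses give 1.10 cm. Equal unrecorded worsening with equal dropout in both arms cancels.
- A reader might infer that nothing else in the plan bears on robustness. There is a per-protocol analysis, and multiple imputation would normally start in the 20% and 30% cases if both arms lost that share. Neither closes the gap: the per-protocol set is defined by sessions and medication, not follow-up attendance, and imputation under the usual MAR assumption also gave 1.10 cm.
- A reader might infer that reported results already carry this error. They do not, because only descriptive statistics can currently be reported.

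Two further limits stand. The figures concern the week-24 contrast, whereas the primary test is the group-by-time interaction over five visits. At the planned dropout rate the bias is modest. What survives is that the documents give no way of knowing in advance whether relapse will be recorded, and no planned analysis examines the case where it is not.

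**Conclusion.** The point holds in conditional form and is worth acting on. Section 9 attaches a promise of robustness to a comparison with an undefined second arm, and nothing in the SAP varies the missing-data assumption toward missing-not-at-random. If benefit is lost unrecorded in the active arm, LOCF, observed-case and MAR analyses share an upward week-24 bias of about 0.11 cm at 10% active-arm loss and 0.22 cm at 20%, against an effect of 1.1 cm. These sizes assume that sham is unchanged and that leavers lose the whole benefit. They do not show that such dropout occurred or will occur. The consequence arises only if the trial resumes and inferential results are produced.

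**What to change.** Before any inferential analysis, revise SAP section 9 as follows.

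1. Define the analysis without LOCF: either a mixed model fitted to all observed VAS scores or multiple imputation under MAR, by arm, from the observed visits. State the imputation model and how the missing rate is counted.
2. Remove the statement that agreement with and without LOCF secures robustness. The comparison may stay as a descriptive check.
3. Add a delta-adjusted (tipping-point) analysis. Raise imputed VAS scores in pre-set steps (for example 0, 0.5, 1.0, 1.5 and 2.0 cm) in the active arm only, the sham arm only, and both arms.
4. At each step report the active-minus-sham difference with its 95% CI, and the step at which the conclusion changes. If it does not change within the range, say so; with about 10% missing that is likely for a 1.1 cm result.
5. State beforehand, with reasons, what size of shift would count as implausible.

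Reference-based imputation would be an acceptable alternative to step 3. The cost is a few lines of SAP text and some extra analysis code, with no new data. The downside is that the reported robustness may look less favourable.

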**Deviation statistical plan:**

The study was unfortunately disrupted due to the impact of COVID-19, which led to its discontinuation. Consequently, we have been limited in our ability to collect and analyze comprehensive data, and are currently only able to report descriptive statistics. We acknowledge that this is a limitation in our findings, and we are exploring potential avenues to resume the study and gather more robust data in the future.

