### 2. Study Design and Groups

- **Design:** Prospective, double-blind, randomized controlled trial with a parallel-group design. This prevents potential carry-over effects from sham to treatment phases.
- **Groups:**
  - **Active tDCS Group:** Real tDCS targeting the occipital nerve at 1.5mA for 20 minutes.
  - **Sham tDCS Group:** Sham tDCS with a brief current sensation to maintain blinding but no sustained current.

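### The SAP's deviation section replaces every between-arm estimate with descriptive statistics, giving neither the number per arm nor a statistical reason

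*SAP*

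**What the plan says.** SAP section 2 describes a "Prospective, double-blind, randomized controlled trial with a parallel-group design". Hypothesis 1, in the protocol summary, is comparative: pain should improve more after real than after sham stimulation. SAP section 6A sets the primary VAS analysis as a "Mixed-effects repeated-measures ANOVA with group (treatment vs. sham) as a between-subjects factor", with time as the within-subjects factor and baseline as one of its five levels. It uses LOCF for the intention-to-treat analysis. Section 9 adds multiple imputation above 10% missing data and a comparison of results with and without LOCF.

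The deviation section at the end of the SAP then states: "The study was unfortunately disrupted due to the impact of COVID-19, which led to its discontinuation". It says the team was "limited in our ability to collect and analyze comprehensive data" and is "currently only able to report descriptive statistics". It calls this a limitation and adds that the team is "exploring potential avenues to resume the study". It does not say how many participants were randomised or analysed in either arm, or whether the descriptive statistics will be split by arm. No between-arm estimate or interval is retained.

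**The concern.** The only reason given is that the pandemic limited data collection. That explains a smaller dataset but does not explain why no contrast can be estimated from it. The documents attribute the stop to an outside event, not to efficacy or safety results, so the stop itself gives no reason to expect bias between the randomised arms.

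Two things are at stake. First, the trial's question is active against sham, and descriptive statistics alone give no effect size with its uncertainty, either for that question or for later evidence synthesis. Second, without a stated contrast, readers are left to judge from change within an arm. In a sham-controlled pain trial that change mixes any treatment effect with placebo response and regression to the mean.

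**Working it through.** **1. The plan's own figure.** SAP section 3 gives 60 participants (30 per group), "allowing an 80% power to detect a 1.1 cm difference on the VAS scale", a significance level of 0.05 and 10% anticipated dropout. It states neither an SD nor sidedness, so 60 cannot be reproduced directly. Solving backwards, two-sided, with d = (1.960 + 0.842) × √(2/n) and SD = 1.1/d:

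- 30 per arm: d = 0.723, SD = 1.52 cm (t-based: d = 0.736, SD = 1.50).
- 27 per arm (30 less 10%): d = 0.762, SD = 1.44 cm (t-based: d = 0.777, SD = 1.42).

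Forward check: SD 1.5 gives 30 per arm, or 60 in all, before dropout. SD 1.4 gives 26 per arm, inflated to 29 (58 in all). The figure therefore fits an SD of about 1.4 to 1.5 cm. Read one-sided, the SD would be 1.60 to 1.71 cm. Section 3 also labels the 1.1 cm as Cohen's d. Taken literally as d = 1.1, only 13 per arm would be needed, so the reading in centimetres is itself an assumption.

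**2. Does a small sample invalidate the interval?** Coverage of the 95% CI from a baseline-adjusted model was simulated with 6,000 trials per size, normal errors, SD 1.5 and correlation 0.5. It was 94.8% at 2 per arm, 95.1% at 3, 95.2% at 5, 94.9% at 10 and 95.0% at 15. Under those conditions validity holds and only width suffers.

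**3. How wide is it?** For n per arm and baseline correlation r, the baseline-adjusted half-width is

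t(0.975, 2n−3) × SD × √(1−r²) × √(2/n) × √(1 + 1/(2n−4)).

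Example with n = 10, SD 1.5 and r = 0.5: 2.110 × 1.5 × 0.866 × 0.447 × 1.031 = 1.26 cm.

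The unadjusted half-width is t(0.975, 2n−2) × SD × √(2/n). At r = 0.5 a contrast of changes from baseline has the same variance, because 2(1−0.5) = 1. That column is therefore a guide to the planned model, where baseline is a time level.

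| n per arm | Adjusted, SD 1.42 | Adjusted, SD 1.5 | Unadjusted, SD 1.42 to 1.5 |
|---|---|---|---|
| 5 | 1.99 | 2.10 | 2.1 to 2.2 |
| 10 | 1.20 | 1.26 | 1.3 to 1.4 |
| 15 | 0.94 | 0.99 | 1.1 |
| 20 | 0.80 | 0.84 | 0.9 to 1.0 |

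(half-widths in cm)

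At 10 per arm the range runs from 0.99 cm (SD 1.42, r = 0.7) to 2.43 cm (SD 2.5, r = 0). At 3 per arm, with SD 1.5 and r = 0.5, it is 4.13 cm. At 2 per arm the simulated median half-width is about 14 cm, more than the whole 10 cm scale.

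**4. Power.** With SD 1.5 and r = 0.5, power for 1.1 cm is about 59% at 15 per arm, 41% at 10 and 19% at 5. An interval is useful at these sizes, but a significance verdict is not.

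**The case against.** The strongest reply is that the achieved number is unknown, data collection was itself limited, and the authors openly call the result a limitation. With two or three participants per arm, or with follow-up lost for reasons tied to treatment, an interval would add little or could mislead. This stands as a condition on the point. The estimate needs both arms, residual degrees of freedom, roughly normal errors when numbers are tiny, and ignorable missingness. None of these can be checked from the documents, which is a further reason to report numbers per arm and visit.

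A second reply is that publishing a contrast now is an unplanned comparative look in a trial the team hopes to resume, so deferring inference is defensible. That also has force. It calls for disclosure of the look. It does not settle how any later participants should be analysed, and several arrangements would be reasonable.

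A third is that baseline adjustment was not pre-specified. That is correct: section 6A treats baseline as a time level, so a baseline-covariate model would be post hoc. Also, if the 1.1 cm referred to change scores, the back-solved SD would already reflect baseline, and the unadjusted column is the safer guide.

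A reader might infer that the randomised comparison has been abandoned for good, or that resumption is being weighed after results by arm were seen. The text supports neither. It describes the current position, leaves resumption open and does not mention arms. If means, SDs and numbers by arm were reported, a reader could form an unadjusted difference and interval, though not a baseline-adjusted one.

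**Conclusion.** The point holds in a limited form. The deviation section drops all between-arm estimation without the number per arm or a statistical reason, and a shortfall caused by an external stop does not by itself justify that.

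The cost is imprecision. With SD 1.4 to 1.5 cm and correlation 0.5, the adjusted half-width falls from about 2.0 to 2.1 cm at 5 per arm to about 0.8 cm at 20. Below about 5 per arm the interval says almost nothing. These figures rest on a back-solved SD, two-sided testing, the reading of 1.1 as centimetres and an assumed correlation. None of these except the 1.1 cm unit is stated, and that unit is blurred by the Cohen's d label.

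Two stronger readings should be avoided. One is that an estimate is valid at any achieved size, since the conditions above must hold. The other is that from 15 per arm the interval is narrower than the 1.1 cm target. It is the adjusted half-width that falls below 1.1 cm there; the full interval is about 1.9 to 2.0 cm wide (2 × 0.94 to 2 × 0.99).

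**What to change.** Add one paragraph to the deviation section:

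- Report the number randomised, and the number with VAS data, per arm and visit.
- Report the active-minus-sham VAS difference at each visit with a 95% CI. Take it from the planned group-by-time mixed model on observed data, or from a baseline-adjusted version labelled post hoc.
- Show results with and without LOCF, as section 9 already plans.
- Label the estimate imprecise and make no claim of efficacy or of no effect. If an arm is empty or the model cannot be fitted, say so and give that as the reason for descriptive reporting.
- If recruitment may resume, disclose that a comparative look has taken place.

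The cost is a few hours of analysis on data already collected and a paragraph of text. The downside is that the interval may be wide, and the report must say so plainly.
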